### **7.3. Other Assessments**

#### **7.3.1. Small Fiber Neuropathy – Symptom Inventory Questionnaire (SFN-SIQ)**

The SFN-SIQ has been developed specifically for evaluation of autonomic symptoms in SFN patients. It includes 13 questions that address the following aspects: presence of palpitations,

flushes, constipation or diarrhea, urination problems (incontinence or hesitation), changes in sweating pattern, restless legs, orthostatic dizziness, dry eyes or mouth, oversensitivity and intolerance to sheets on legs and burning feet. Responses are graded as “never”, “sometimes”, “often” or “always”.

### **7.3.2. Brief Pain Inventory-Short Form (BPI-sf)**

The Brief Pain Inventory-Short Form (BPI-sf) is a self-administered questionnaire developed to assess pain severity and pain interference with functional activities during a 24 hour period prior to evaluation. Four questions assess pain severity on an 11-point scale ranging from “no pain” (0) to “pain as bad as you can imagine” (10): worst pain in the past 24 hours, least pain in the past 24 hours, average pain in the past 24 hours and current pain (“right now”). Seven items assess pain interference with functional activities: general activity, mood, walking ability, normal work (includes both work outside the home and housework), relations with other people, sleep and enjoyment of life. These items are also measured on an 11-point scale, ranging from “does not interfere” (0) to “completely interferes” (10). The Brief Pain Inventory-Short Form will be completed by the subject at all scheduled face to face visits.

### **7.3.3. Sleep Score from the Daily Sleep Diary (NRS-Sleep)**

Pain-related sleep interference will be assessed on an 11-point numerical rating scale

(NRS Sleep) ranging from 0 (did not interfere with sleep) to 10 (completely interfered [unable to sleep due to pain]). Subjects are to describe how their pain has interfered with their sleep during the past 24 hours by choosing the appropriate number between 0 and 10. The NRS-Sleep is included in the subject electronic diary and self-assessment will be performed daily upon awakening from baseline to the end of the study.

### **7.3.4. Patient Global Impression of Change (PGIC)**

The PGIC is a subject rated global measure that provides a clinically relevant and easy to interpret account of a patient’s perception of the clinical importance of their improvement or worsening during their involvement in a clinical study. Subjects rate their overall improvement on a 7-point scale where scores range from 1 (very much improved) to 7 (very much worse).

The PGIC is recommended by the Initiative on Methods, Measurement, and Pain Assessment in Clinical Trials (IMMPACT) as a measure of “participant rating of global improvement and satisfaction with treatment.” It is one of six core outcomes measures recommended for use in clinical trials of chronic pain treatment efficacy and effectiveness. The PGIC will be completed by the subject at Visits 5 and 6. Completion instructions for subjects will indicate that global improvement refers to the condition under study.

### **7.3.5. EuroQol-5D (EQ-5D)**

The EQ-5D is a brief health status measure used in clinical and health economic appraisals (The EuroQol Group, 1990). The EQ-5D comprises of 5 items that assess the level of difficulty (none, some, severe) subjects report in 5 health status domains: mobility, self-care, usual

activities, pain/discomfort and anxiety/depression. The EQ-5D also includes a visual analogue scale that rates the patient's current perception of overall health status that is scored from 0 (worst imaginable health state) to 100 (best imaginable health state). It takes approximately 2-5 minutes to complete.

### **7.3.6. Proteomics, Lipidomics and Metabolomics analysis**

Proteomics and Lipidomics are large scale study of proteins and lipids in biological systems. These techniques are being extensively used to determine biomarkers of the disease, as well predictors of the response to treatment. Metabolomics is the scientific study of chemical processes involving metabolites. Specifically, metabolomics is the systematic study of the unique chemical fingerprints that specific cellular processes leave behind by studying their small-molecule metabolite profiles. The metabolome represents the collection of all metabolites in a biological cell, tissue, organ or organism, which are the end products of cellular processes. Thus, while proteomic analyses do not tell the whole story of what might be happening in a cell, metabolic profiling can give an instantaneous snapshot of the physiology of that cell. By using these methods, we hope to find biomarkers of idiopathic small fiber neuropathy, as well as predictors of response to treatment.

## **7.4. Safety Assessments**

### **7.4.1. Laboratory Assessments**

- Samples for laboratory testing will be analyzed by laboratory.
- Tests required at Visit 1 are:
- Hematology: hemoglobin, hematocrit, WBC count including differential (neutrophils, lymphocytes, monocytes, eosinophils, basophils), red blood cell (RBC) count, platelet count.
- Chemistry: amylase, aspartate aminotransferase (AST), alanine aminotransferase (ALT), albumin, alkaline phosphatase, blood urea nitrogen, creatinine, electrolytes (sodium, potassium, chloride, calcium), glucose, total protein, total bilirubin, uric acid,
- Fasting plasma glucose and HbA1C
- A standard 3-mm dermatologic punch biopsy for intraepidermal small fiber nerve assessment if not done previously
- Thyroid-stimulating hormone (TSH) with reflex T4 done if TSH abnormal,
- B12/Folate.
- HIV Elisa (confirm with Western Blot if positive)
- Hep C Ab
- SED rate (ESR)
- RPR or similar test for syphilis

- CLcr will be estimated from creatinine at baseline using the Cockcroft and Gault equation:

$$CLcr = \frac{[140 - \text{age (years)}] \times \text{weight (kg)}}{[72 \times \text{Serum creatinine (mg/dl)}]} \quad (\text{x 0.85 for female patients})$$

SI Units:

$$CLcr = \frac{[1.23 \times [140 - \text{age (years)}] \times \text{weight (kg)}]}{\text{Serum creatinine (\mu moles/l)}} \quad (\text{x 0.85 for female patients})$$

- Monitoring for Hy's Law (Drug-Induced Hepatotoxicity)

Every effort should be made to ensure that the protocol required tests and procedures are completed as described. However it is anticipated that from time to time there may be circumstances, outside of the control of the investigator that may make it unfeasible to perform the test. In these cases the investigator will take all steps necessary to ensure the safety and wellbeing of the subject. When a protocol required test cannot be performed the investigator will document the reason for this and any corrective and preventive actions which he/she has taken to ensure that normal processes are adhered to as soon as possible. The study team will be informed of these incidents in a timely fashion.

#### 7.4.2. Physical and Neurological Examination

Physical examinations at Screening/Visit 1 and every clinic visit afterwards will include the following:

- General appearance (including height at baseline).
- Skin (examination for the presence of rash).
- HEENT (examination of head, eyes, ears, nose, and throat).
- Chest (auscultation of lung fields).
- Cardiovascular (auscultation of heart sounds [S1 and S2] and for the presence of murmurs, gallops, or rubs).
- Gastrointestinal (abdominal rigidity and tenderness).
- Edema assessment (severity of any peripheral edema, presence of generalized/abdominal edema or facial/periorbital edema).

Additional physical assessments may be performed as necessary to evaluate subjects. Any clinically significant negative changes from the entry examination should be recorded as an adverse event.

### 7.4.3. Neurological Examination

Neurological exam (including examination of mental status, motor function, sensory function, coordination) will be conducted at Screening (Visit 1) and end of study or in the event of early termination ET.

As part of the neurological exam a specific neuropathic pain assessment is to be conducted to assess eligibility for the study.

Patients will be assessed for the following:

- Mental status exam for short term memory, alertness, orientation, ability to do simple calculations and serial 7's, demonstrates comprehension of the concept of a numerical rating scale for pain severity.
- Burning, stabbing or tingling sensation/pain in the feet
- Numbness
- Increased or decreased temperature sensation
- Self-report of hypersensitivity to touch, heat, or cold
- Pin prick perception in feet and legs
- Increased or decreased sharp sensation (eg, pinprick testing);
- Position sense for big toe
- Vibratory sensation with 128 Hz tuning for at large toe;
- Reflexes: patellar, biceps, and Achilles
- Motor strength for toe dorsiflexion, and any evidence of muscle wasting in legs or arms
- Screening only: Complete and submit a copy of the neuropathic pain eligibility worksheets. The neuropathic pain eligibility worksheet should be kept in the subject's source documentation.
- For quality assurance purposes, Pfizer, or its designated representative, may review and validate subject eligibility based on the Screening neurological examination and neuropathic pain assessment, painDETECT, skin biopsy results, and worksheets. Subjects may be deemed eligible or ineligible based upon this review.
- painDETECT: painDETECT is a questionnaire that was developed to detect neuropathic components of pain. Exploratory analyses of efficacy results will be conducted based on painDetect scores at Screening (Visit 1). The painDETECT will also assist the clinician in confirming that the patient has a symptom profile that is consistent with small fiber neuropathy though no specific score is required for inclusion.

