#### **6.2.5.1. Discontinuation**

- Patients discontinuing from the study will complete a taper. Dispense a bottle of taper medication to the patient and schedule a Follow-Up phone visit.

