#### **6.2.6. Visits 7 (at Weeks 14) – Clinic Visits**

- Review adverse events, the daily pain and sleep diary, the dosing diary, concomitant medications, and non-drug treatments. Confirm that the patient is taking one study medication capsule twice daily. Remind the patient to continue completing diaries daily.
- The C-SSRS will be completed by the patient and reviewed to determine if a risk assessment is required.
- Perform the following assessments: SFN-SIQ questionnaire, BPI-SF, and EQ-5D
- Dispense a bottle of taper medication to the patient and provide instructions for dose administration.
- Schedule a follow-Up phone visit.

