### **6.3. Subject Withdrawal**

Subjects may withdraw from the study at any time at their own request, or they may be withdrawn at any time at the discretion of the investigator or sponsor for safety, behavioral, or administrative reasons. If a subject does not return for a scheduled visit, every effort should be made to contact the subject. In any circumstance, every effort should be made to document

subject outcome, if possible. The investigator should inquire about the reason for withdrawal, request the subjects to return all unused investigational product(s), request the subjects to return for a final visit, if applicable and follow-up with the subject regarding any unresolved adverse events.

If the subject withdraws from the study, and also withdraws consent for disclosure of future information, no further evaluations should be performed, and no additional data should be collected. The investigator may retain and continue to use any data collected before such withdrawal of consent.

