### **9.1.1. Analysis of Primary Endpoint**

- To evaluate efficacy, we will compare the endpoint mean pain score for the Lyrica group compared to the placebo group using an analysis of covariance (ANCOVA) model with treatment and center as main effects and the baseline PI score as a covariate.
- A BOCF and a modified or hybrid approach (mBOCF) will be used to account for missing data at last treatment Week. As a sensitivity we will look at the LOCF, MMRM and the missing imputation (suggested the National Academy of Sciences report).

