### **9.1.2. Analysis of Secondary Endpoints**

Secondary analyses included examination of the PGIC and sleep interference rate will be compared between treatment groups using a Cochran-Mantel-Haenszel test.

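### The final visit for patients who leave early has no listed assessments, so a randomised patient who leaves before Visit 7 has no scheduled post-randomisation value on PGIC, BPI-sf, EQ-5D or SFN-SIQ, and no missing-data rule covers these endpoints

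*Combined protocol and SAP*

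**What the plan says.** Three places refer to an assessment at early departure. Section 7.4.3 sets the neurological examination at screening, at study end and at early termination: it "will be conducted at Screening (Visit 1) and end of study or in the event of early termination ET". Section 6.3 asks the investigator to "request the subjects to return for a final visit, if applicable and follow-up with the subject regarding any unresolved adverse events". Section 7.2.1.1 runs the daily diary to a Visit 10 or termination, although the schedule in Appendix 1 ends at Visit 7. Appendix 1 has no early-termination column, and no part of Section 6 lists procedures for such a visit.

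The only post-randomisation clinic visit is Visit 7, where Section 6.2.6 says: "Perform the following assessments: SFN-SIQ questionnaire, BPI-SF, and EQ-5D". Section 7.3.2 says that BPI-sf "will be completed by the subject at all scheduled face to face visits", which does not clearly cover an unscheduled departure visit.

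On analysis, Section 9.1.1 names BOCF and a modified BOCF, which "will be used to account for missing data at last treatment Week", with LOCF, MMRM and imputation as sensitivity analyses. All of this stands under the primary endpoint. Section 9.1.2 says only that "PGIC and sleep interference rate will be compared between treatment groups using a Cochran-Mantel-Haenszel test". It gives no analysis set and no missing-data rule.

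**The concern.** Secondary objectives 1 and 2 (global assessment and quality of life) rest on PGIC and EQ-5D, and BPI-sf and SFN-SIQ are listed beside them as secondary endpoints. Daily pain and sleep interference are collected by diary up to the day a patient leaves. These four questionnaires are not, so a value missed at departure cannot be recovered.

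The plan expects departures after randomisation. Under Section 5, a patient whose pain becomes intolerable may be withdrawn for lack of efficacy. A patient who cannot tolerate the lowest dose level leaves, and so does anyone who needs a dose adjustment in the withdrawal phase. Lack of efficacy is more likely on placebo and intolerance on pregabalin, so the two arms may lose different kinds of patient. With 20 planned per group, each leaver is 1/20 = 5% of an arm.

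**Working it through.** **1. What is scheduled after randomisation.** Appendix 1 makes Visit 6 both the last single-blind visit and the randomisation visit, so Visit 6 values are not outcomes of the randomised comparison.

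| Instrument | Section 6.2.6 (Visit 7) | Section 7 | Appendix 1 | Scheduled for a leaver before Visit 7 |
|---|---|---|---|---|
| BPI-sf | listed | scheduled face-to-face visits | V7 | none |
| EQ-5D | listed | no timing given | V7 | none |
| SFN-SIQ | listed | no timing given | V7 | none |
| PGIC | not listed | Visits 5 and 6 (7.3.4) | last two marks, read as V6 and V7 | none |

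The PGIC row holds a second problem. Taken literally, 7.3.4 gives no post-randomisation rating even to patients who complete, and 6.2.6 does not supply one. Only Appendix 1 does.

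**2. Whether 9.1.1 could simply be extended.** Not without a decision. PGIC is a rating of change with no entry at Visit 1 or 2, so it has no baseline to carry forward. Carrying Visit 6 values forward would give both arms a value taken on pregabalin.

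**3. Possible size of the bias.** The plan has no figure to reproduce here: it states neither a dropout rate nor a PGIC response rate. The inputs below are assumptions. PGIC is improved in p = 60% (pregabalin) and 35% (placebo) of all randomised patients, a difference of 25 points. A proportion d leaves, and a proportion q of leavers had improved. The rate among those who reach Visit 7 is

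c = (p − q·d) / (1 − d).

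Example with d = 10% and 30%, q = 0: 0.60/0.90 = 66.7%; 0.35/0.70 = 50.0%; difference 16.7.

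| Leavers, pregabalin / placebo | q | Pregabalin | Placebo | Difference (points) |
|---|---|---|---|---|
| 10% / 10% | 0 | 66.7% | 38.9% | 27.8 |
| 20% / 20% | 0 | 75.0% | 43.8% | 31.3 |
| 10% / 20% | 0 | 66.7% | 43.8% | 22.9 |
| 10% / 30% | 0 | 66.7% | 50.0% | 16.7 |
| 10% / 40% | 0 | 66.7% | 58.3% | 8.3 |
| 10% / 20% | 15% | 65.0% | 40.0% | 25.0 |
| 10% / 30% | 15% | 65.0% | 43.6% | 21.4 |

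The difference can shrink, stay the same or grow.

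**4. Loss of precision.** The 20 per group comes from Section 9.1 and is used here only as the planned arm size. Whether it gives the stated power for pain is a separate question. With n per arm at Visit 7, the standardised difference detectable with 80% power (two-sided 0.05) is (1.960 + 0.842)·√(2/n):

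- n = 20 (no loss): 0.89
- n = 18 (10% lost): 0.93
- n = 16 (20% lost): 0.99
- n = 14 (30% lost): 1.06

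**5. Power by simulation.** Assumptions: 20 per arm, a 7-category score, a latent shift of 0.8 SD, a rank test standing in for the Cochran-Mantel-Haenszel test, and 10% leaving on pregabalin. Power with all patients is about 65%. Ranges cover repeated runs.

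| Placebo leavers | Worst outcomes leave | Leaving partly related to outcome | Leaving unrelated to outcome |
|---|---|---|---|
| 20% | 56–57% | 51–52% | 57% |
| 30% | 37–40% | 39–42% | 54% |
| 40% | 24–25% | 27–32% | 50% |

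At 20% placebo leavers, strict removal of the worst outcomes costs no more power than plain loss of numbers. The large losses need 30–40% leaving on placebo.

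**The case against.** Several stronger readings are tempting, and the documents do not support them.

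- **That the plan has no visit for leavers.** Section 6.3 does ask the investigator to "request the subjects to return for a final visit, if applicable". The gap is its undefined content and timing. Questionnaires could be taken there; none is scheduled.
- **That the plan specifies a completers-only analysis.** It does not. That is the default when no rule is stated. Section 9.1.2 names a test only for PGIC and sleep interference, and sleep is a diary item. For BPI-sf, EQ-5D and SFN-SIQ no between-group test is stated at all.
- **That Section 6.2.5.1 shows randomised leavers get only a taper and a call.** Its instruction, "Dispense a bottle of taper medication to the patient and schedule a Follow-Up phone visit", stands under Visit 6 and concerns patients who are not randomised. Their Visit 6 questionnaires are already done, and they never enter the drug–placebo comparison.
- **That leavers have no safety assessment.** Sections 7.4.2 and 7.4.4 put the examination (with oedema), weight and vital signs at every clinic visit after screening, which can include a final visit. Visits 3 to 5 may be moved to the clinic to assess an adverse event. C-SSRS has no such clause.
- **That the treatment difference must shrink.** With equal dropout and unimproved leavers, the table shows it growing.

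It can also be objected that these are secondary endpoints with no power claim, and that replacing a Day 84 value by an earlier one, or classing leavers as not improved, is one choice of estimand among several. Both points stand. In particular, patients randomised to placebo are still on a pregabalin taper in the first week of the withdrawal phase, so a value taken then need not reflect placebo. This limits how departure values should be used. It is no reason not to collect them.

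**Conclusion.** The point holds in this form: the content of the early-termination or final visit is undefined, a randomised patient who leaves before Visit 7 has no scheduled value on four secondary instruments, and no missing-data rule covers those endpoints. A Visit 7 comparison would by default use only patients who reach Visit 7, and it would be biased if leaving is unequal between arms and related to outcome. Section 5 makes that plausible. Neither the direction nor the size can be settled from the documents. The 8.3 to 31.3 point range against 25 rests wholly on assumed response and dropout rates. The primary pain endpoint and sleep interference are less affected, because the diary runs until departure. The change should be made before patients are randomised, since the data cannot be obtained later.

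**What to change.** 1. Add an early-termination column to Appendix 1 and a matching subsection in Section 6. List the Visit 7 assessments there: PGIC, BPI-sf, EQ-5D, SFN-SIQ, C-SSRS, physical examination with oedema, weight and vital signs, beside the neurological examination of 7.4.3. Do them at the final visit that 6.3 already requests, and record the date.
2. In the same amendment, reconcile the PGIC timing in 7.3.4, 6.2.6 and Appendix 1. A between-group comparison in the withdrawal phase needs a rating after randomisation. An early-termination column alone does not settle this.
3. In 9.1.2, state the analysis set and how early-termination values are used, with at least one analysis that includes all randomised patients. Treat the classing of lack-of-efficacy leavers without a rating as not improved as a sensitivity analysis. Note that values from the first week after randomisation fall within the pregabalin taper.

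Cost: one table column, a short subsection, the PGIC corrections and a few sentences in 9.1.2. No new visit is needed. The downside is a few more questionnaires per leaver, and values taken before Day 84.

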#### **7.4.4. Vital Signs**

Vital signs (sitting heart rate and blood pressure, weight; height at Screening only) will be obtained at Screening visit and every clinic visit afterwards.

### **7.5. Suicidality Assessment**

#### **7.5.1. Patient Health Questionnaire-8 (PHQ)**

The PHQ-8 is a self-administered version of the PRIME-MD diagnostic instrument for common mental disorders. The PHQ-9 is the depression module, which scores each of the 9 DSM-IV criteria as 0 (not at all) to 3 (nearly every day). The PHQ-8, a validated subset of the PHQ-9 (the first 8 items of the PHQ-9) will be completed by subjects at Screening (Visit 1).

#### **7.5.2. Columbia Suicidal Severity Rating Scale(C-SSRS)**

This semi-structured interview was originally developed to evaluate the link between antidepressants and suicidal behavior and ideation in youth, adverse events from pediatric clinical trials. C-SSRS is utilized in current study to provide a summary measure of suicidal risks.

##### **7.5.2.1. Risk Assessment During Screening**

The Investigator will review the results of the C-SSRS (baseline), and medical history. The following criteria would indicate a potential suicide risk:

- The subject may have had suicidal ideation associated with actual intent and/or plan in the past year based on C-SSRS assessment.

**Note:** in an event a suicidal ideation is identified in baseline C-SSRS, the Investigator should inquiry the timeframe of the event and determine whether it occurred during the past year.

- Any previous lifetime history of suicide behaviors based on C-SSRS assessment.
- Investigator's judgment that a risk assessment is required.

If any of these criteria are met the subject is considered not eligible to participate in the trial.

Beginning with Visit 2, if there are any positive responses on C-SSRS (since last visit), a risk assessment should be done by a qualified mental health provider. Suicidal risk should be managed appropriately by the Investigator together with a qualified MHP. In addition, the Investigator should consult with the Pfizer medical monitor to determine whether the subject can continue the trial.

A suicidal narrative should be constructed for subjects who have undergone any post-baseline risk assessment, using information from the C-SSRS and should be kept as a source document.

